## **Measures**

### **Demographic measures**

Demographic measures collected at baseline will include: date of birth, sex, postcode, employment status, ethnicity, referral reason, referring professional, and number of previous referrals.

### **Outcome measures**

aAll patient outcome data will be collected at two time-points: pre-intervention (prior to an induction with an ERP) and at Week 12 (post 12-week consultation with an ERP). bAt 6-month follow-up, **questionnaire-based measures and PA levels** (determined by an accelerometer worn for 7 days), **only** will be collected. All data will be collected and analysed by a researcher at LJMU. All outcome measures were piloted in a previous study (REF 16/WA/0231) and were deemed acceptable by patients and demonstrated adequate sensitivity to detect change.

a Collected at Baseline and week 12

b Collected at Baseline, week 12 and 6-month follow-up

a **Cardiorespiratory Fitness.** A sub-maximal VO2 test (Astrand Rhyming test) will be carried out to estimate cardiorespiratory fitness. The Astrand Rhyming test allows you to predict VO2max from work intensity and heart rate. Following a warm-up (unloaded cycling 3-5 minutes at 50-60 rpm) the procedure will begin. Using a Polar Heart Rate Monitor to measure heart rate, the individual will begin cycling at 60 rpm with a workload of 60 watts (female) or 90 watts (male). The participant will then cycle at this workload for 6 minutes. Heart rate will be measured each minute; blood pressure will be measured at each 3-minute period as well as pre- and post-test. If the mean heart rate is between 125 and 170 beats per minute at minute 5 and 6, the test can be terminated. If the mean heart rate is less than 125 beats per minute, the workload will be increased by 30 watts (0.5 kg). If the mean heart rate is less than 125 beats per minute at minute 5 and 6 the test will be continued for a further 3 minutes. This procedure will be repeated until the required heart rate is achieved. The test will be stopped if the participant experiences any adverse effects, their heart rate exceeds recommended max heart rate values for this test, or if the participant wants to stop.

b **Objective PA levels.** Objective PA will be analysed using an accelerometer (ActiGraph software), which will be fitted during baseline testing at LJMU. A baseline 7-day monitoring period will occur before participants engage with the scheme. During the 7-day monitoring period, each participant will complete a diary to record hours of use as well as distinguish between work and leisure hours.

a **Endothelial function.** Flow-mediated dilation (FMD) and carotid vasoreactivity (cold pressor test) will measure artery function. These tests have been deemed non-invasive and strong predictors of CVD risk (Cunningham & Gotlieb, 2005; Rubenfire *et al.*, 2000). The primary researcher will conduct these ultrasound tests with assistance and training from experts in the field of cardiovascular physiology ([name]).

*Flow mediated dilation.* Endothelium dependent vasodilatation of the brachial arteries will be examined using ultrasound. Brachial artery baseline diameter and blood flow will be assessed in one arm. An ultrasound probe is placed on the bicep for 1 minute before a blood pressure cuff (placed around the forearm)

is inflated to suprasystolic pressure (~220 mmHg) for 5 minutes. Immediately after the cuff is deflated, changes in arterial diameter and flow will be assessed continuously for 3 minutes using the ultrasound probe.

**Carotid vasoreactivity.** The carotid vasoreactivity (cold pressor) test will measure the carotid artery's response to a stimulus. Similar to the method above, an ultrasound probe will be placed on the patient's left side of their neck, positioned in such a way to allow a clear image of the right common carotid artery to be displayed on the ultrasound monitor screen. The cold pressor procedure involves submersion of the left hand to wrist in ice slush for 180-seconds. Ultrasound data will then be analysed post hoc.

**a Blood Profiles.** A 15ml blood sample will be taken. The primary researcher for this study will complete all phlebotomy and has completed the relevant LJMU training as well as having previous experience working as a physiologist collecting blood samples among other health-related measures. Blood profiles will be analysed as a measure of cardiometabolic health. Analysis will be conducted at LJMU. Patients will be made aware of the storage and use of their tissue. Blood analysis will include: glucose, insulin, cholesterol (Total, HDL and LDL), lipids, triglycerides, CRP and homocysteine.

**b Lifestyle questionnaire.** Information regarding patients' lifestyle will be collected via questions related to dietary habits (e.g. number of fizzy drinks per week, amount of processed meat etc.), alcohol consumption, smoking status, as well as any services the patient may be receiving lifestyle support from.

**b Self-reported PA.** Patients' perceived PA levels will be recorded with the short version of the International Physical Activity Questionnaire (IPAQ, Craig et al., 2003). The short-IPAQ is a 7-day recall self-administered tool that measures intensity, frequency and duration of PA and provides a total estimate of energy expenditure. A total score of MET-minutes/day/week and sedentary behaviour minutes/day/week will be calculated according to the IPAQ scoring protocol.

**b Psychological wellbeing.** Psychological wellbeing will be measured using the Warwick-Edinburgh Mental Well-being Scale (WEMWBS, Tennant et al., 2007). WEMWBS is a 14-item positively worded instrument containing items related to psychological functioning (e.g. "I've been thinking clearly") and subjective well-being (e.g. "I've been feeling cheerful"). Participants are asked to rate on a Likert scale of 1 (none of the time) to 5 (all of the time) how well each statement describes their experiences over the last two weeks.

**b PA motivation.** The Behavioural Regulation in Exercise Questionnaire (BREQ-2, Markland & Tobin, 2004) plus 4 additional items (Wilson et al., 2006a) will be used to assess PA motivation. The BREQ-2 is a widely-used instrument comprised of 19 items describing reasons why people exercise (e.g. "I think exercising is a waste

of time”; “I feel ashamed when I miss an exercise session”; “I exercise because it’s fun”). Participants answer on a likert scale of 0 (not true for me) to 4 (very true to me) to indicate how true each item is for them.

b **Psychological needs satisfaction.** Psychological need satisfaction will be measured using the Psychological Need Satisfaction in Exercise Scale (PNSE, Wilson et al., 2006b). The PNSE is an 18-item instrument designed to measure participants’ perceived autonomy (e.g. “I feel free to exercise in my own way”), competence (e.g. “I feel capable of completing exercises that are challenging to me”) and relatedness (e.g. “I feel connected to the people who I interact with while we exercise together”) in an exercise context. Participants are asked to answer on a 6-point likert scale (1 = false, 6 = true) to indicate how they typically feel when they exercise.

b **Perceived needs support.** Needs support will be measured using a 15-item needs support (NS) tool developed by Markland and Tobin (2010) to measure the extent to which participants perceive their exercise instructors provide support for autonomy, structure (linked to competence) and involvement (linked to relatedness).

b **Intentions to engage in PA.** Three items developed by Edmunds et al. (2007) will be used to assess patients’ intentions to engage in PA (e.g. “I plan to regularly engage in PA during the next 3 months”).

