## Recruitment

### ***Intervention and usual care conditions***

Eligible patients will be recruited from Centre A and Centre B (after they have been referred to the ERS by a health professional). Once referred, it is standard protocol that ERS patients visit their chosen *Lifestyles* fitness centre to book an ERS induction with administrative staff. During this initial contact, administrative staff will introduce the study briefly and provide the individual with a summary poster (attached). If the patient is interested, administrative staff will gain verbal consent to pass the patient's contact details to the researcher (NB this is consent for sharing details only, the participant will still have the opportunity to opt out before full research consent is sought). Administrative staff will then provide patients with the participant information sheet to take away and have some time to consider. Patients will be informed that the researcher will contact them within one week to discuss the study and check if they want to take part. Researcher contact details will be provided on the poster and information sheet in case the participant has any questions in the meantime.

For patients who consent to speak to the researcher, the administrative staff will book an ERS induction 2-3 weeks later (to allow time for the patient to undergo baseline testing prior to starting the ERS). The researcher will then contact the patient to arrange a visit to Liverpool John Moores University (LJMU) laboratories for baseline collection of health measures.

Patients who opt out of the study at this stage will continue with the ERS as usual.

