#### ***No treatment control condition***

Participants in the no treatment control group will be recruited via posters placed around LJMU, electronic invitations on LJMU research recruitment websites, email communications to LJMU staff and students, and LJMU social media output (see attached documents). Interested participants will contact the researcher for further information, who will e-mail them a full participant information sheet. If the participant then decides to take part the researcher will arrange a date and time to visit LJMU laboratories for baseline collection of health measures.

**Participant blinding.** Due to the nature of the study, it will not be possible to fully blind patients to their study condition (as they will know whether they are signed up to attend an ERS or not) or to blind ERS staff (who will know whether their centre is the intervention or the usual care condition). Patients within the two active conditions (intervention and usual care) will not however be informed whether their centre is the intervention or the usual care condition.

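### No masking of assessor, image reader or analyst is stated, although stored ultrasound could be read under random codes and the two ERS arms analysed under neutral labels

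*Combined protocol and SAP*

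**What the plan says.** All references are to the combined protocol and SAP.

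- **Outcome measures**, on who handles the data: "All data will be collected and analysed by a researcher at LJMU". On the vascular tests: "The primary researcher will conduct these ultrasound tests with assistance and training from experts in the field of cardiovascular physiology". On blood samples: "The primary researcher for this study will complete all phlebotomy".
- **Outcome measures**, end of the carotid vasoreactivity paragraph: "Ultrasound data will then be analysed post hoc". The flow-mediated dilation (FMD) paragraph has no equivalent sentence.
- **Recruitment, Intervention and usual care conditions**: centre administrative staff pass on the details of patients who agree, and "The researcher will then contact the patient to arrange a visit".
- **Recruitment, No treatment control condition**: controls come through university advertising, and "Interested participants will contact the researcher for further information".
- **Participant blinding** (same section): "it will not be possible to fully blind patients to their study condition". Patients in the two ERS arms "will not however be informed whether their centre is the intervention or the usual care condition". ERS staff are described as impossible to blind. Nothing is said about whoever measures, reads or analyses.
- **Analyses**: linear mixed models with baseline values and other covariates that are not named; a distribution check with no stated consequence; magnitude-based inferences with no stated thresholds.

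**The concern.** The reason given for not blinding patients and staff is that they cannot avoid knowing which scheme they attend or deliver. That reason does not apply to a stored ultrasound recording or to a data set. Where reading takes place after the visit, the reader need not know whose scan it is, which arm it belongs to, or whether it is baseline or week 12.

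Two steps are open to expectation. Measuring arterial diameter from ultrasound involves judgement. The model leaves choices open that an analyst who sees the arms could make after seeing their effect. Arms in this trial are defined by centre or recruitment source, so confounding is already a concern. A reading bias that differs by arm would add to it and could not be separated from a treatment effect afterwards.

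**Working it through.** **1. Does any passage provide masking?** The blinding paragraph names two groups, patients and ERS staff. The descriptions of ultrasound, blood analysis and accelerometry, and the Analyses section, mention neither coded files nor coded arms. The gap is therefore real.

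**2. Does the researcher know the arm?** No sentence says so. Set side by side, the passages make it very probable:
- ERS patients' details reach the researcher from the centre where they booked, and centre defines arm.
- Controls contact the researcher directly, by a different route.
- Patient procedure has ERS patients return the accelerometer to the practitioner at Centre A or Centre B, while controls return it to the university. The instructions therefore differ at least between ERS patients and controls.

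Centre is settled before the baseline visit, so this knowledge would be present at both scans.

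**3. Which steps can be masked?**

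| Step | Can coding reach it? |
|---|---|
| Reading stored carotid scans | Yes; reading after the visit is stated |
| Reading stored FMD scans | Yes, if they too are read afterwards; to be confirmed |
| Acquiring the scans | No |
| Cardiorespiratory fitness (live cycle test) | No |
| Model choice, intervention vs usual care | Yes; target sizes are equal (70 and 70) |
| Model choice, any contrast with control | No; 30 against 70 identifies the control arm |

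**4. How large could the effect be?** The documents give no figure for reading bias, so this is an illustration on assumed values.

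Inputs from Sample size estimation: difference 1.98, SD 3.2, alpha 0.05, power 0.8, 84 evaluable, 140 recruited, 40% dropout. Sidedness is not stated; two-sided is assumed.

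The plan's figure is reproduced first. A two-sample t-test with 1.98/3.2 = 0.619 SD needs 41.98, so 42 per arm and 84 in total; 84/(1 − 0.40) = 140. Masking changes neither number.

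Let b be a systematic between-arm reading bias in SD units. With 42 per arm, the standard error of the difference is √(2/42) = 0.218 SD. When there is no true effect, the two-sided error rate is

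Φ(b/0.218 − 1.96) + Φ(−b/0.218 − 1.96)

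| Assumed b (SD) | b / SE | True error at nominal 5% |
|---|---|---|
| 0.1 | 0.46 | 7.4% |
| 0.2 | 0.92 | 15.0% |
| 0.3 | 1.37 | 28.0% |

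This takes 42 evaluable per arm for the vascular outcomes too, although the plan derives that number for fitness. It ignores any precision gained from baseline adjustment.

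**The case against.** The strongest reply is that the remedy reaches little of what matters most. The Objectives name cardiorespiratory fitness at 12 weeks as the effectiveness outcome. It comes from a live submaximal test, and masked scan files cannot affect how that test is run. The vascular outcomes are not named in the Objectives. The fitness estimate uses monitor heart rate and set workloads, and activity is recorded by accelerometer, so those outcomes leave less to a reader's discretion. This stands and limits the point.

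Neutral labels are also an imperfect mask. The control arm shows by its size, and probably by referral reason and referring professional. Consultations at weeks 4, 8 and 18 occur only at Centre A, so linked process data would separate the two ERS arms. This stands too: labels work only between the ERS arms, and only in a data set without process data. Naming covariates in advance is the more direct cure for open model choices, and neutral labels do not replace it.

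A reader might infer that one person does everything. The text says only a researcher at LJMU. Experts assist with ultrasound, practitioners record consultation attendance, and several team members review the qualitative data. No passage says that the person who reads diameters also chooses the model terms.

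A reader might also take the researcher's knowledge of arm as documented, or expect coded files to remove reader bias. The first is an inference from recruitment. The second fails because the primary researcher performs the scans and, if also the reader, may recognise images; influence during scanning is untouched.

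**Conclusion.** The point holds in limited form. The protocol states no masking of assessor, image reader or analyst, and the researcher very probably knows the arm. Offline ultrasound reading, and the model choices for the intervention versus usual care comparison, are therefore exposed to avoidable bias in a non-randomised trial. Coding would reduce that bias without removing it. It leaves bias during scanning and in the live fitness test as it was, and it cannot mask the control arm.

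The size of the bias cannot be derived from the documents. The 7.4% to 28.0% range shows only what assumed biases of 0.1 to 0.3 SD would do at 42 per arm; it is not evidence that such bias will occur. The conclusion rests on two assumptions: that the recruitment routes reveal the arm to the researcher, and that reading after the visit, stated in the carotid paragraph, applies to FMD as well. If FMD is measured only during the visit, the scan remedy covers carotid reactivity alone. This is a worthwhile low-cost improvement and not a defect that invalidates the design.

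**What to change.** 1. State whether FMD recordings, like the carotid ones, are stored and read after the visit.
2. Before any reading, rename the stored scans by script to random codes that hide participant, arm and visit. If names or dates appear within the files, remove those too.
3. Have the same reader work through the files in random order, mixing arms and visits. Another existing team member holds the key until all reading is complete.
4. For intervention versus usual care, replace the two arm names with neutral labels in a data set without process data, until the primary model (covariates and structure) is fixed in writing. State that the control arm cannot be masked this way.
5. Add a sentence to the blinding paragraph saying who is and is not masked, and acknowledging that scanning and the fitness test remain unmasked.

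Cost: a renaming script, a key file and a short delay before reading. No extra assessor is needed and the sample size is unchanged. That the cost is small is a judgement; the documents give no figure. The change must come before reading and model fitting begin, because it loses most of its value afterwards.

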### Process Measures (intervention and usual care groups, unless otherwise noted)

**Attendance at consultations.** Patient attendance records will be collected by ERPs at the following time-points:

- Intervention centre: induction, 4,8,12 and 18 weeks;
- Usual care centre: induction and 12 weeks.

**Attendance at fitness centre.** The number of times patients sign in at the leisure centre to go to either the gym or a class will be recorded on a weekly basis for weeks 1 to 12, then on a monthly basis up to 6 months. This information is automatically recorded at leisure centres when patients visit.

**Patient focus groups.** Focus groups will be conducted with a purposeful subsample of patients after approximately 6-12 weeks of attending the scheme (e.g. those with low attendance, high attendance, significant health changes, no change etc.). Two focus groups will be conducted with patients attending the intervention centre (approx 5-8 participants per group) and two focus groups will be conducted with patients attending the usual care centre (approx 5-8 participants per group) (20-32 participants in total). Focus groups will be conducted at the individual fitness centres and will last approximately 60 minutes. Discussion will focus on the extent to which, and how, patients feel each ERS is facilitative (or not) in helping them become more

physically active, with questions about staff interactions, activities on offer, and the impact of the scheme on their likely continuation with PA.

**ERP interviews (intervention group only).** ERPs from the *intervention centre only* will take part in a semi-structured interview (after over half of patients have reached the 18-week point) to explore the acceptability of the co-developed intervention and any challenges of delivery, areas that require further development etc.

**Fidelity.** Fidelity of intervention delivery will be measured in two ways:

1. ERPs from both intervention and usual care centres will be asked to monitor the number of consultations offered (measured by appointment bookings or records of appointments offered but declined by participants), and the number of consultations conducted for each patient.
2. A random sample of ERS inductions from both intervention and usual care centres (approx 10 per centre) plus a random sample of 4, 8, 12 and 18-week consultations from the intervention centre only will be audio-recorded and coded for the use of “needs-supportive” communication strategies (using a coding manual developed through a previous pilot study (REF 16/WA/0231)). In addition, all intervention centre recordings will be coded for fidelity to an agreed protocol, e.g. asking required questions about physical activity, setting an action plan, giving out patient log book etc.

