### *Between-group effects (ERS arms vs no treatment control)*

It is estimated that a larger effect size would occur between the ERS arms and the no treatment control, it was therefore decided we did not need to recruit as many participants. To identify a difference of 3.2 units ( $\text{ml.kg.min}^{-2}$ ; 0.3 units smaller than the within-subjects change seen in the previous pilot for fitness to allow for some variance) between the ERS arms and a no treatment control arm a sample of 17 would be required ( $f=0.5$ ,  $p=0.05$ , power = 0.8). Factoring for dropout witnessed in the pilot study (40%) this yields a sample of 30 patients for the no treatment control arm.

In summary, the study will aim to recruit 70 patients for the intervention condition, 70 for the usual care condition and 30 for the no treatment control.

*ERPs.* All ERPs responsible for delivering the ERS at Centre A (n=4-5) and Centre B (n=2-3) will be invited to take part.

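### Fidelity recordings are drawn without regard to practitioner, so a Centre A practitioner may well have no recorded induction; sampling within practitioner removes this with the same number of recordings

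*Combined protocol and SAP*

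**What the plan says.** Fidelity of delivery is one of the stated objectives. Under Process Measures it is measured in two ways.

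- **Counts.** "ERPs from both intervention and usual care centres will be asked to monitor the number of consultations offered" and the number conducted for each patient. This covers every practitioner but not what happens in the consultation.
- **Recordings.** "A random sample of ERS inductions from both intervention and usual care centres (approx 10 per centre"). For Centre A the sentence goes on: "plus a random sample of 4, 8, 12 and 18-week consultations from the intervention centre only will be audio-recorded". No number is given for these follow-up recordings. Recordings are coded for needs-supportive communication, and in addition "all intervention centre recordings will be coded for fidelity to an agreed protocol".

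Neither sample is stratified by practitioner, and no minimum per practitioner is set. The size of the team is given under Sample size estimation: "All ERPs responsible for delivering the ERS at Centre A (n=4-5) and Centre B (n=2-3) will be invited to take part". The pool of inductions follows from the recruitment target in the same section: "the study will aim to recruit 70 patients for the intervention condition, 70 for the usual care condition".

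**The concern.** What is coded is largely something the individual practitioner does or does not do: how they talk to patients, whether they set an action plan, whether they hand out the log book. The practitioner is therefore the natural sampling stratum. Ten recordings spread by chance over four or five people can leave someone out and fall mostly on one or two others. The result would then be reported for the centre while describing only part of the team.

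The trial has one intervention centre and a small team, so with equal caseloads a single practitioner delivers 20-25% of the inductions. If cardiorespiratory fitness shows no difference between the ERS arms, the fidelity data will be used to judge whether the scheme was delivered as intended. A result with gaps in coverage supports that judgement less well.

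**Working it through.** The figure of about 10 per centre comes with no derivation or coverage target, so there is nothing to reproduce. The check is how well 10 random draws cover the team.

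**Inputs from the protocol.** n = 10 recorded inductions per centre; 4-5 practitioners at Centre A and 2-3 at Centre B; 70 patients per ERS arm.

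**Assumptions.** One induction per recruited patient, so N = 70; a simple random sample, since the text says only that it is random; and the caseload splits below, since none is given.

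**Formula.** If practitioner *i* conducts c_i of the N inductions, the chance that none of theirs is drawn is C(N − c_i, n) / C(N, n). The chance that at least one practitioner is missed follows by inclusion-exclusion: the sum of these single terms, minus the sum over pairs (with c_i + c_j in place of c_i), plus the sum over triples, and so on.

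**Example, five practitioners with 14 inductions each.**
- Single term: C(56,10)/C(70,10) = 0.0898; times 5 = 0.4488.
- Ten pairs: 0.0371 in total. Ten triples: 0.0003 in total.
- Result: 0.4488 − 0.0371 + 0.0003 = 0.412.

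**Chance that at least one practitioner has no recorded induction.**

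| Centre | Caseloads | Probability |
|---|---|---|
| A | 18/18/17/17 (equal) | 17.5% |
| A | 14 × 5 (equal) | 41.2% |
| A | 28/21/14/7 (assumed) | 41.1% |
| A | 35/21/7/7 (assumed) | 56.9% |
| A | 28/14/14/7/7 (assumed) | 65.9% |
| A | 28/18/10/7/7 (assumed) | 68.1% |
| B | 35/35 (equal) | 0.1% |
| B | 24/23/23 (equal) | 3.6% |
| B | 40/21/9 (assumed) | 24.6% |

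If the pool is much larger than 70, sampling with replacement is the limit. The equal-caseload figures for Centre A then become 21.9% and 47.7%. With equal caseloads and N = 70, the chance that some Centre A practitioner has at most one recorded induction is 74% (four) or 98% (five), by simulation.

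**Adding the Centre A follow-up recordings.** Their number is unstated, so I took two values, with the same caseload shares and sampling with replacement. The chance that some practitioner is never recorded at all is:

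| Caseload shares | 10 inductions + 10 follow-ups | 10 inductions + 40 follow-ups |
|---|---|---|
| 4 equal | 1.3% | below 0.1% |
| 5 equal | 5.7% | below 0.1% |
| 40/30/20/10% | 13.3% | 0.5% |
| 40/20/20/10/10% | 25.2% | 1.0% |

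**Cost of stratifying.** For a caseload-weighted mean, the within-practitioner design effect is n × Σ(W_i² / n_i), where W_i is the caseload share and n_i the number of recordings. Take 28/18/10/7/7, with shares 0.400, 0.257, 0.143, 0.100 and 0.100.
- Two recordings each: 10 × 0.2665/2 = 1.33, an effective n of about 7.5.
- Allocation 4/2/2/1/1: 10 × (0.0400 + 0.0331 + 0.0102 + 0.0100 + 0.0100) = 1.03, an effective n of about 9.7.

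Allocation roughly in proportion to caseload therefore loses almost nothing, whereas a fixed two each would lose about a quarter of the effective sample under this split.

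**The case against.** The case against is substantial, and much of it stands.

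- **Follow-up recordings.** A reader might infer that Centre A practitioners can easily go wholly unrecorded. The documents do not support that. Follow-up consultations at Centre A are also recorded, and enough of them would make a complete miss rare. What remains is that their number is not fixed and that they cannot stand in for the induction. At Centre A the induction is where suitability for the 18-week intervention is explored and alternatives are offered. It is also the only consultation recorded at both centres, so any comparison of communication style between centres rests on it.
- **Bias.** A reader might infer that fidelity will be overstated. It will not be in general: a random sample of inductions weights itself by caseload and is unbiased on average. Missing a strong practitioner understates fidelity just as missing a weak one overstates it. With uneven caseloads the person most likely to be missed is one with few inductions; missing someone with 7 of 70 leaves 90% of inductions represented.
- **Other evidence on delivery.** A reader might infer that the trial could not tell failure of the scheme from failure of delivery. That goes too far. Patients rate the support they perceive from instructors, consultations are counted for each patient, focus groups cover staff interactions, and Centre A practitioners are interviewed about delivery. None of these is an observation of protocol content, so they reduce the gap without closing it.
- **Assumptions.** The uneven caseloads are mine, and a random sample as worded does not exclude stratification. The equal-caseload figures, the favourable case, are the ones to rely on.

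**Conclusion.** The concern holds as a point of coverage and precision. As worded, the plan leaves an 18% (four practitioners) or 41% (five) chance that at least one Centre A practitioner has no recorded induction, assuming equal caseloads, 70 inductions and a simple random draw. Under the assumed uneven caseloads the range is about 41-68%. At Centre B the risk is small with equal caseloads (0.1-4%).

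It does not show that practitioners will go wholly unrecorded, that fidelity will be systematically overstated, or that delivery failure would be undetectable. It bears on the process evaluation only. This is a cheap improvement to the design, not a flaw that threatens the trial.

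**What to change.** Amend item 2 of the Fidelity paragraph as follows.

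1. Keep the total of about 10 inductions per centre, but draw them at random within practitioner, roughly in proportion to caseload and with at least one for each practitioner who consents to be recorded. With equal caseloads this gives 3/3/2/2 or 2 each at Centre A, and 5/5 or 4/3/3 at Centre B.
2. Sample the Centre A week 4, 8, 12 and 18 recordings in the same way, and state how many are planned.
3. Weight the centre mean by caseload wherever the allocation is not proportional.

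Every consenting practitioner then has a recorded induction by design, and differences between practitioners no longer add to the sampling error through chance imbalance in who is recorded. Practitioners are only invited to take part, so any who decline should be reported as not covered.

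No extra recordings are needed. The costs are a simple weight and some scheduling work, because inductions must be selected from each practitioner's bookings and the allocation adjusted as caseloads become known. One to three recordings for most Centre A practitioners are too few to report fidelity for each one, so the result should stay at centre level.
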